5. SELECTION OF PATIENTS

5.1. Inclusion Criteria

Patients will be considered for inclusion in this study if they meet all of the following criteria:

1. Men and women \geq 18 years of age
2. Eastern Cooperative Oncology Group (ECOG) performance status of 0-1
3. Diagnosis of CLL/SLL that meets published diagnostic criteria ([Hallek 2008](#)):
 - a) monoclonal B-cells (either kappa or lambda light chain restricted) that are clonally co-expressing at least one B-cell marker (CD19, CD20, or CD23) and CD5
 - b) Prolymphocytes may comprise no more than 55% of blood lymphocytes
 - c) There is no evidence of cyclin D1 rearrangement or BCL-1 over expression
4. Active disease meeting at least 1 of the following IWCLL 2008 criteria for requiring treatment:
 - a) Evidence of progressive marrow failure as manifested by the development of, or worsening of, anemia (Hgb $<$ 10 g/dL) and/or thrombocytopenia (platelets $<$ 100,000/ μ L)
 - b) Massive (ie, at least 6 cm below the left costal margin), progressive, or symptomatic splenomegaly
 - c) Massive nodes (ie, at least 10 cm in the longest diameter), progressive, or symptomatic lymphadenopathy
 - d) Progressive lymphocytosis with an increase of more than 50% over a 2-month period or a lymphocyte doubling time (LDT) of less than 6 months. LDT may be obtained by linear regression extrapolation of absolute lymphocyte counts (ALC) obtained at intervals of 2 weeks over an observation period of 2 to 3 months. In patients with initial blood lymphocyte counts of less than $30 \times 10^9/L$ (30,000/ μ L), LDT should not be used as a single parameter to define indication for treatment. In addition, factors contributing to lymphocytosis or lymphadenopathy other than CLL (eg, infections) should be excluded
 - e) Autoimmune anemia and/or thrombocytopenia that is poorly responsive to standard therapy (see [Appendix K](#))
 - f) Constitutional symptoms documented in the patient's chart with supportive objective measures, as appropriate, defined as one or more of the following disease-related symptoms or signs:
 - i) Unintentional weight loss \geq 10% within the previous 6 months prior to Screening
 - ii) Fevers higher than 100.5°F or 38.0°C for 2 or more weeks prior to Screening without evidence of infection
 - iii) Night sweats for more than 1 month prior to Screening without evidence of infection

5. Must have received at least one prior therapy for CLL/SLL and not be appropriate for treatment or retreatment with purine analog based therapy, defined by at least one of the following criteria:
 - a) Failure to respond (stable disease [SD] or disease progression on treatment), or a progression-free interval of less than 3 years from first dose of treatment with a purine analog based therapy and anti-CD20 containing chemoimmunotherapy regimen after at least two cycles
 - b) Age ≥ 70 years, who had received >1 prior treatment including at least two cycles of an alkylating-agent based (or purine analog based) anti-CD20 antibody containing chemoimmunotherapy regimen or ≥ 2 prior lines of systemic therapy including chemotherapy, anti-CD20 or anti-CD52 monoclonal antibodies, or immunomodulatory therapy with lenalidomide or thalidomide
 - c) Age ≥ 65 years with co-morbidities, who had received ≥ 1 prior treatment including at least two cycles of an alkylating-agent based (or purine analog based) anti-CD20 antibody containing chemoimmunotherapy regimen. Co-morbidities are defined by at least one of the following:
 - i) Estimated creatinine clearance (ie, estimated Glomerular Filtration Rate, eGFR using) Cockcroft-Gault < 70 mL/min
 - ii) Platelet count $< 100,000/\mu\text{L}$ or hemoglobin < 10 g/dL
 - iii) History of clinically significant autoimmune cytopenia (controlled autoimmune hemolytic anemia or immune thrombocytopenia as defined in [Appendix K](#))
 - iv) Eastern Cooperative Oncology Group (ECOG) performance score = 1
 - d) History of purine analog-associated autoimmune anemia or autoimmune thrombocytopenia temporally associated (within 4 weeks) of treatment with a purine analog
 - e) The presence of 17p deletion by FISH
6. Measurable nodal disease by computed tomography (CT). Measurable nodal disease is defined as at least one lymph node > 1.5 cm in the longest diameter in a site that has not been previously irradiated. An irradiated lesion may be assessed for measurable disease only if there has been documented progression in that lesion since radiotherapy has ended
7. Meet the following laboratory parameters:
 - a) Absolute neutrophil count (ANC) ≥ 750 cells/ μL ($0.75 \times 10^9/\text{L}$) and independent of growth factor support 7 days prior to assessment
 - b) Platelet count $\geq 30,000$ cells/ μL ($30 \times 10^9/\text{L}$) without transfusion support 7 days prior to assessment. Patients with transfusion-dependent thrombocytopenia are excluded
 - c) Serum aspartate transaminase (AST/SGOT) or alanine transaminase (ALT/SGPT) < 2.5 x upper limit of normal (ULN)
 - d) Total bilirubin ≤ 1.5 x ULN (unless due to Gilbert's syndrome or patients with autoimmune hemolytic anemia that is otherwise controlled)

- e) Estimated creatinine clearance (ie, estimated Glomerular Filtration Rate, eGFR) using Cockcroft-Gault ≥ 30 mL/min
- 8. Able to provide written informed consent and can understand and comply with the requirements of the study
- 9. Able to receive all outpatient treatment, all laboratory monitoring, and all radiological evaluations at the institution that administers study drug for the entire study
- 10. Female patient of childbearing potential must have a negative serum or urine pregnancy test within 3 days of the first dose of study drug and agree to use dual methods of contraception during the study and for 1 month following the last dose with ibrutinib or 12 months following the last dose with ofatumumab. Post menopausal females (>45 years old and without menses for >1 year) and surgically sterilized females are exempt from this criterion
- 11. Male patient must use an effective barrier method of contraception during the study and for 3 months following the last dose if sexually active with a female of childbearing potential

5.2. Exclusion Criteria

Patients will be ineligible for this study if they meet any of the following criteria:

- 1. Known central nervous system (CNS) lymphoma or leukemia
- 2. Known prolymphocytic leukemia or history of or currently suspected Richter's transformation
- 3. Missing or incomplete documentation of cytogenetic and/or FISH results reflecting the presence or absence of 17p del and the percentage of cells with the deletion in patient records prior to randomization
- 4. Uncontrolled autoimmune hemolytic anemia (AIHA) or idiopathic thrombocytopenic purpura (ITP) defined as declining hemoglobin or platelet count secondary to autoimmune destruction within the screening period or requirement for high doses of steroids (>20 mg daily of prednisone daily or equivalent). See [Appendix K](#).
- 5. Prior exposure to ofatumumab or to ibrutinib (PCI-32765) or randomization into an ibrutinib study
- 6. Received any chemotherapy, external beam radiation therapy, anticancer antibodies, or investigational drug within 30 days prior to first dose of study drug
- 7. Corticosteroid use > 20 mg within 1 week prior to first dose of study drug, except as indicated for other medical conditions such as inhaled steroid for asthma, topical steroid use, or as premedication for administration of study drug or contrast. Patients requiring steroids at daily doses > 20 mg prednisone equivalent systemic exposure daily, or those who are administered steroids for leukemia control or white blood cell count lowering are excluded
- 8. Radio- or toxin-conjugated antibody therapy within 10 weeks prior to first dose of study drug

9. Prior autologous transplant within 6 months prior to first dose of study drug
10. Prior allogeneic stem cell transplant within 6 months prior to randomization or with any evidence of active graft versus host disease or requirement for immunosuppressants within 28 days prior to first dose of study drug.
11. Major surgery within 4 weeks prior to first dose of study drug
12. History of prior malignancy, with the exception of the following:
 - a) Malignancy treated with curative intent and with no evidence of active disease present for more than 3 years prior to Screening and felt to be at low risk for recurrence by treating physician
 - b) Adequately treated lentigo maligna melanoma without current evidence of disease or adequately controlled non-melanomatous skin cancer
 - c) Adequately treated cervical carcinoma in situ without current evidence of disease
13. Currently active clinically significant cardiovascular disease such as uncontrolled arrhythmia, congestive heart failure, any Class 3 or 4 cardiac disease as defined by the New York Heart Association Functional Classification ([Appendix J](#)), or history of myocardial infarction within 6 months prior to first dose with study drug
14. Unable to swallow capsules or disease significantly affecting gastrointestinal function and/or inhibiting small intestine absorption such as; malabsorption syndrome, resection of the small bowel, or poorly controlled inflammatory bowel disease affecting the small intestine
15. Uncontrolled active systemic fungal, bacterial, viral, or other infection (defined as exhibiting ongoing signs/symptoms related to the infection and without improvement, despite appropriate antibiotics or other treatment) or ongoing intravenous anti-infective treatment
16. Known history of infection with human immunodeficiency virus (HIV)
17. Serologic status reflecting active hepatitis B or C infection. Patients with hepatitis B core antibody positive who are surface antigen negative or who are hepatitis C antibody positive will need to have a negative polymerase chain reaction (PCR) result prior to enrollment. Those who are hepatitis B surface antigen positive or hepatitis B PCR positive and those who are hepatitis C PCR positive will be excluded.
18. History of stroke or intracranial hemorrhage within 6 months prior to randomization.
19. Pregnant or lactating women
20. Current life-threatening illness, medical condition, or organ system dysfunction which, in the Investigator's opinion, could compromise the patient's safety or put the study at risk
21. Requires or receiving anticoagulation with warfarin or equivalent vitamin K antagonists (eg, phenprocoumon) within 28 days of first dose of study drug
22. Requires treatment with a strong CYP3A4/5 inhibitor

6. TREATMENTS

Patients will be randomized 1:1 to either Treatment Arm A or B.

Treatment Arm A: Ofatumumab IV

Treatment is 12 IV doses over 24 weeks or until disease progression, unacceptable toxicity, or the patient meets any criteria specified in [Section 10](#), whichever occurs first. Administration of ofatumumab will be in accordance with the manufacturer's package insert.

Treatment Arm B: Ibrutinib PO

Treatment is 420 mg (3 x 140-mg capsules) administered orally daily to continue until disease progression, unacceptable toxicity, or the patient meets any criteria specified in [Section 10](#), whichever occurs first.

6.1. Ofatumumab

6.1.1. Dosage and Administration

6.1.1.1. Premedication

Patients should be premedicated 30 minutes to 2 hours prior to each dose of ofatumumab with 975-1000 mg acetaminophen/paracetamol; 10 mg Cetirizine orally or equivalent antihistamine, either IV or oral; and 100 mg IV prednisolone or equivalent corticosteroid.

Corticosteroid dose reduction:

- Do not reduce corticosteroid dose for ofatumumab infusions 1, 2, or 9.
- Corticosteroid doses may be reduced as follows:

For Doses 3 through 8:

- If infusion-related reaction \geq Grade 3 experienced, do not reduce corticosteroid dose for subsequent doses.
- If infusion-related reaction $<$ Grade 3 experienced, may consider gradually reducing corticosteroid dose with subsequent doses.

For Doses 10 through 12:

- If infusion-related reaction \geq Grade 3 experienced with Dose 9, do not reduce corticosteroid dose for subsequent doses.
- If infusion-related reaction $<$ Grade 3 experienced with Dose 9, may consider administering prednisolone 50 – 100 mg (or its equivalent) for subsequent doses.

Ofatumumab infusion premedication should be administered as outlined above and consistent with the package insert. It is recognized that some institutional variation to these procedures may exist, however for the purposes of this study; the package insert instructions must be followed. Routine infusion premedication with corticosteroid doses of $>$ 100 mg IV prednisolone (or equivalent) is not permitted.

6.1.1.2. Dosage Regimen and Administration

Ofatumumab should be diluted in 0.9% Sodium Chloride Injection, USP and administered as an IV infusion. Do not administer the drug as an IV push or bolus.

The ofatumumab dosage and schedule is 12 doses administered as follows

Week 1: 300 mg initial dose

Weeks 2 through 8: 2,000 mg given weekly

Weeks 12, 16, 20 and 24: 2,000 mg every 4 weeks

An observation period following the end of infusion should occur as per the institution's standard practice. Refer to the [Arzerra[®] package insert](#) for additional administration instructions.

6.1.2. Dose Delay

Treatment with ofatumumab should be held for any unmanageable, potentially study drug-related toxicity that is Grade 3 or greater in severity. Additional information concerning dose delays can be found in Section 6.1.4.

Any other clinically important events where dose delays may be considered appropriate by the investigator must be discussed with the Medical Monitor.

Study drug may be held for a maximum of 28 days from expected dose due to toxicity. Study treatment should be discontinued in the event of a toxicity lasting > 28 days, unless reviewed and approved by the Medical Monitor.

6.1.3. Dose Interruption

Interrupt infusion for infusion-related reactions of any severity. For Grade 4 infusion-related reactions, do not resume the infusion. For Grade 1, 2, or 3 infusion-related reactions, if reaction resolves or remains \leq Grade 2, resume infusion including increasing infusion rate consistent with the package insert according to the initial Grade of the infusion reaction:

- Grade 1 or 2: Infuse at one-half of the previous infusion rate
- Grade 3: Infuse at a rate of 12 mL/hour

6.1.4. Dose Discontinuation

The actions in [Table 1](#) should be taken for the following toxicities:

- Grade 4 ANC ($< 500/\mu\text{L}$) for > 7 days (Neutrophil growth factors are permitted per ASCO guidelines [[Smith 2006](#)] and use must be recorded in the case report form [CRF]).
- Grade 3 or 4 platelets ($< 50,000/\mu\text{L}$); or, in patients with baseline thrombocytopenia, a platelet decrease of 50-74% from baseline in presence of significant bleeding
- Grade 4 Platelets ($< 25,000/\mu\text{L}$); or, in patients with baseline thrombocytopenia, decrease of $\geq 75\%$ from baseline or $< 20,000/\mu\text{L}$, whichever is higher

- Grade 3 or 4 nausea, vomiting, or diarrhea, if persistent despite optimal antiemetic and/or anti-diarrheal therapy
- Any other Grade 4 toxicity or unmanageable Grade 3 toxicity.

Table 1: Dose Discontinuation Actions for Ofatumumab

Occurrence	Action
1 st -3 rd	Hold ofatumumab until recovery to Grade \leq 1 or baseline; may restart at original dose level
4 th	Discontinue ofatumumab

In addition, discontinue ofatumumab if progressive multifocal leukoencephalopathy (PML) is suspected.

All patients will be screened for hepatitis B and those with evidence of chronic or active infection will be excluded from the protocol. However, if a patient develops viral hepatitis, they should be discontinued from ofatumumab treatment.

6.1.5. Dose Reduction

As dose reductions are not outlined in the package insert, dose reductions are not allowed for ofatumumab during this study.

6.1.6. Precautions and Adverse Effects

6.1.6.1. Warnings and Precautions

Infusion-Related Reactions: Premedication and infusion parameters, as outlined in the package insert should be used. Monitor patients closely during infusions and interrupt infusion if any reaction occurs.

Cytopenias: Monitor blood counts as outlined in the Schedule of Assessments ([Appendix A](#)).

6.1.6.2. Adverse Events

The most common serious adverse events (SAEs) with ofatumumab were infections (including pneumonia and sepsis), neutropenia, and pyrexia. Infections were the most common AEs leading to drug discontinuation. Additional common AEs (\geq 10%) with ofatumumab were cough, diarrhea, anemia, fatigue, dyspnea, rash, nausea, bronchitis, and upper respiratory tract infections.

6.2. Ibrutinib

6.2.1. Dosage and Administration

Ibrutinib 420 mg (3 x 140-mg capsules) is to be administered orally once daily with 8 ounces (approximately 240 mL) of water. The capsules should be swallowed intact and patients should not attempt to open capsules or dissolve them in water.

Each dose of ibrutinib should be taken at approximately the same time each day. Patients should avoid consuming food and beverages containing grapefruit juice or Seville oranges for the duration of the study due to CYP3A4/5 inhibition. If a dose is missed, it can be taken as soon as possible on the same day with a return to the normal schedule the following day.

Ibrutinib will be dispensed to patients in bottles. Unused ibrutinib dispensed during previous visits must be returned to the site and drug accountability records ([Section 13.8](#)) updated at each visit. Returned capsules must not be redispensed to anyone. Ibrutinib should not be dispensed to anyone other than a patient enrolled in the study and can only be dispensed in its original bottle.

6.2.2. Dose Delay

Treatment with ibrutinib should be held for any unmanageable, potentially study drug-related toxicity that is Grade 3 or higher in severity. Please see [Section 6.6.1.4](#) for guidelines for management of ibrutinib in patients who require anticoagulant treatment.

Any other clinically important events where dose delays may be considered appropriate by the investigator must be discussed with the Medical Monitor.

Study drug may be held for a maximum of 28 consecutive days for toxicity. Study treatment should be discontinued in the event of a toxicity lasting >28 days, unless reviewed and approved by the Medical Monitor.

6.2.3. Overdose

Any dose of study drug administered in excess of that specified in this protocol is considered to be an overdose. Signs and symptoms of an overdose that meet any SAE criterion must be reported as a SAE in the appropriate time frame and documented as clinical sequelae to an overdose.

There is no specific experience in the management of ibrutinib overdose in patients. No maximum tolerated dose (MTD) was reached in the Phase 1 study in which subjects received up to 12.5 mg/kg/day (1400 mg/day). Healthy subjects were exposed up to single dose of 1680 mg. One healthy subject experienced reversible Grade 4 hepatic enzyme increases (AST and ALT) after a dose of 1680 mg. Subjects who ingested more than the recommended dosage should be closely monitored and given appropriate supportive treatment.

Refer to [Section 9.3](#) for further information regarding AE reporting.

6.2.4. Dose Reduction and Discontinuation

The actions in Table 2 should be taken for the following toxicities:

- Grade 4 ANC (< 500/ μ L) for > 7 days (Neutrophil growth factors are permitted per ASCO guidelines [Smith 2006] and use must be recorded in CRF).
- Grade 3 or 4 platelets (< 50,000/ μ L); or, in patients with baseline thrombocytopenia, a platelet decrease of 50-74% from baseline in presence of significant bleeding
- Grade 4 Platelets (< 25,000/ μ L); or, in patients with baseline thrombocytopenia, decrease of \geq 75% from baseline or < 20,000/ μ L, whichever is higher
- Grade 3 or 4 nausea, vomiting, or diarrhea, if persistent despite optimal antiemetic and/or anti-diarrheal therapy
- Any other Grade 4 toxicity or unmanageable Grade 3 toxicity.

For Grade 3 or 4 atrial fibrillation or persistent atrial fibrillation of any grade, consider the risks and benefits of ibrutinib treatment. If clinically indicated, the use of anticoagulants or antiplatelet agents may be considered for the thromboprophylaxis of atrial fibrillation (Section 6.6.1.4).

Table 2: Drug Discontinuation Actions for Ibrutinib

Occurrence	Action
1 st	Hold ibrutinib until recovery to Grade \leq 1 or baseline; may restart at original dose level
2 nd	Hold ibrutinib until recovery to Grade \leq 1 or baseline; restart at one dose level lower (280 mg daily)
3 rd	Hold ibrutinib until recovery to Grade \leq 1 or baseline; restart at one dose level lower (140 mg daily)
4 th	Discontinue ibrutinib

Dose changes must be recorded in the Dose Administration CRF.

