6.2.6. Dose Modification for Hepatic Impaired Subjects

Ibrutinib is metabolized in the liver and therefore subjects with clinically significant hepatic impairment at the time of screening (Child-Pugh class B or C) are excluded from study participation. For subjects who develop mild liver impairment while on study (Child-Pugh class A), the recommended dose reduction for ibrutinib/placebo is to a level of 280 mg daily (two capsules). For subjects who develop moderate liver impairment while on study (Child-Pugh class B), the recommended dose reduction is to a level of 140 mg daily (one capsule). Subjects who develop severe hepatic impairment (Child-Pugh class C) must hold study drug until resolved to moderate impairment (Child-Pugh class B) or better. Monitor subjects for signs of toxicity and follow dose modification guidance as needed (Refer to [Appendix L](#)).

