6.6.1.1. Guideline for Use of CYP Inhibiting/Inducing Drugs

Ibrutinib is metabolized primarily by CYP3A4. Avoid co-administration with strong or moderate CYP3A inhibitors and consider alternative agents with less CYP3A inhibition. Co-administration of ketoconazole, a strong CYP3A inhibitor, in 18 healthy subjects increased dose normalized exposure, C_{max} and AUC_{0-last} , of ibrutinib by 29- and 24-fold, respectively. The maximal observed ibrutinib exposure (AUC) was ≤ 2 -fold in 37 patients treated with mild and/or moderate CYP3A inhibitors when compared with the ibrutinib exposure in 76 patients not treated concomitantly with CYP3A inhibitors. Clinical safety data in 66 patients treated with moderate (n=47) or strong CYP3A inhibitors (n=19) did not reveal meaningful increases in toxicities. Strong inhibitors of CYP3A (eg, ketoconazole, indinavir, nelfinavir, ritonavir, saquinavir, clarithromycin, telithromycin, itraconazole, and nefazadone) should be avoided. If a strong CYP3A inhibitor must be used, consider reducing the ibrutinib to 140 mg or withhold treatment temporarily. Subjects should be monitored for signs of ibrutinib toxicity. If the benefit outweighs the risk and a moderate CYP3A inhibitor must be used, reduce ibrutinib to 140 mg for

the duration of the inhibitor use. Monitor subject for toxicity and follow dose modification guidance as needed. For subjects who are already on a moderate CYP3A inhibitor concomitantly with ibrutinib without significant toxicity the investigator may consider the overall risk-benefit to determine if a dose reduction of ibrutinib is appropriate. Avoid grapefruit and Seville oranges during ibrutinib treatment, as these contain moderate inhibitors of CYP3A (see [Section 6.2.1](#)). No dose adjustment is required in combination with weak CYP3A inhibitors.

Co-administration of ibrutinib with strong CYP3A inducer, rifampin, in healthy subjects decrease ibrutinib plasma concentration by approximately 10-fold. Avoid concomitant use of strong CYP3A inducers (eg, carbamazepine, rifampin, phenytoin, and St. John's Wort). Consider alternative agents with less CYP3A induction.

A list of common CYP3A inhibitors and inducers is provided in [Appendix C](#); a comprehensive list of inhibitors, inducers, and substrates may be found at <http://medicine.iupui.edu/clinpharm/ddis/main-table/>. This website is continually revised and should be checked frequently for updates.

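### The fixed doses in Protocol Table 2 fit only a patient who starts at 420 mg, and nothing says how the table applies to a patient already reduced to 280 or 140 mg

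*Protocol*

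**What the plan says.** The standard regimen is in Protocol Section 6.2.1: "Ibrutinib 420 mg (3 x 140-mg capsules) is to be administered orally once daily".

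Table 2 in Section 6.2.4 sets the response to listed toxicities by occurrence. In the first three rows ibrutinib is held until recovery, and the restart differs:

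- First: "may restart at original dose level".
- Second: "restart at one dose level lower (280 mg daily").
- Third: "restart at one dose level lower (140 mg daily").
- Fourth: ibrutinib is stopped.

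Other parts of the protocol lower the dose for different reasons:

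- Section 6.2.6, mild impairment (Child-Pugh A) developing on study: "the recommended dose reduction for ibrutinib/placebo is to a level of 280 mg daily (two capsules"). Moderate impairment (Child-Pugh B): "the recommended dose reduction is to a level of 140 mg daily (one capsule"). The section adds: "Monitor subjects for signs of toxicity and follow dose modification guidance as needed".
- Section 6.6.1.1 sets 140 mg while a moderate CYP3A inhibitor that must be used is being taken, and follows this with: "Monitor subject for toxicity and follow dose modification guidance as needed". With a strong inhibitor, 140 mg is one option to consider and a temporary hold is the other. A patient already taking a moderate inhibitor without significant toxicity is left to the investigator's risk-benefit judgement.
- Appendix C, footnotes a and b, sets 140 mg with posaconazole and with voriconazole.

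**The concern.** Each reduced-dose row of Table 2 carries two instructions: a relative one in words and an absolute one in milligrams. They agree only if the patient entered the table at 420 mg. The protocol itself creates patients who do not, and it refers the liver-impaired and the moderate-inhibitor patients back to dose modification guidance. Table 2 is the only stepwise ibrutinib dose table for toxicity in the protocol.

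The patients concerned had their dose lowered because higher exposure is expected, and they have since had a second or third qualifying toxicity. A safety table should not be open to two readings at that point. There is a lesser reporting consequence. Section 10.1 makes stopping mandatory for toxicity as defined in these sections, and Section 12.9 summarises dose reductions. Both rest on a table whose meaning is unsettled for this subgroup.

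**Working it through.** **Inputs.** Standard dose 420 mg, three 140 mg capsules (Section 6.2.1). Named doses 280 mg and 140 mg at the second and third occurrence (Table 2). Reduced doses in force: 280 mg (Child-Pugh A) and 140 mg (Child-Pugh B) from Section 6.2.6; 140 mg from Section 6.6.1.1 and Appendix C.

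**Step 1: reproduce the table for a full-dose patient.** In one-capsule steps the levels are 420, 280 and 140 mg. From 420 mg, one step down is 280 mg (280/420 = 0.67). From 280 mg, the next is 140 mg (140/280 = 0.50). Table 2 is correct for this patient.

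**Step 2: apply the same rows to a patient already reduced.** The ratio is the dose named in the row divided by the dose in force.

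| Dose in force | Occurrence | Named dose | Ratio | Does the figure match the words? |
|---|---|---|---|---|
| 280 mg | Second | 280 mg | 280/280 = 1.00 | No: unchanged |
| 280 mg | Third | 140 mg | 140/280 = 0.50 | Yes |
| 140 mg | Second | 280 mg | 280/140 = 2.00 | No: double |
| 140 mg | Third | 140 mg | 140/140 = 1.00 | No: unchanged |

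The 280 mg starting point arises only from mild liver impairment, since the inhibitor text names only 140 mg. From 140 mg the words cannot be followed either, because no lower level is defined.

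**Step 3: set the second-occurrence figure against the other sections.** While moderate liver impairment or the relevant inhibitor use continues, the 280 mg in Table 2 also disagrees with the 140 mg in Section 6.2.6, Section 6.6.1.1 or Appendix C, whichever applies.

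**Step 4: first occurrence.** The row allows a restart at the original level. For a patient already reduced, that could mean 420 mg or the dose being taken when the toxicity occurred. No section settles it.

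**Step 5: look for a resolving passage.** The appendix that Section 6.2.6 cites (Appendix L) contains only the Child-Pugh score and no dosing. No section explains how Table 2 works below 420 mg.

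**The case against.** A reader might infer that the protocol orders a doubled dose after toxicity. The text does not support that. The row's words call for a decrease, and the bracketed figure is right for the standard patient. Section 6.6.1.1 keeps the 140 mg in place for as long as the moderate inhibitor is used, and Section 6.2.3 treats anything above the specified dose as an overdose. A careful investigator would probably see the bracket as an example for 420 mg. This stands: the defect is a contradiction, not a clear instruction to increase. It does not remove the point, because no passage says which part of the row governs.

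Other limits also stand:

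- The liver reductions are recommended, not required, and the strong-inhibitor reduction is optional. Not every such patient will be below 420 mg.
- In Section 6.6.1.1 the reference to dose modification guidance follows the moderate-inhibitor instruction. After the strong-inhibitor instruction there is only a call to monitor for toxicity. Neither Section 6.2.6 nor Section 6.6.1.1 names Section 6.2.4, so the link to Table 2 is an inference, though a strong one with no other stepwise table available.
- It is tempting to turn the AUC ratios in Section 1.3.1 into exposure multiples for these patients. Those ratios come from single-dose administration, and proportional exposure is reported there only for 420 to 840 mg/day, so 140 and 280 mg lie outside the range.
- A reader might also assume that sites have handled such patients differently. The documents give no evidence of that.
- The SAP bases the final analysis on a data extract of 26 November 2018, so an amendment may have little left to govern in this study.

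**Conclusion.** The contradiction is real and is wrong as written. Below 420 mg, three of the four combinations of current dose and occurrence in the table above give a figure that is not a reduction. One of them is twice the current dose and also conflicts with the 140 mg set elsewhere. The first-occurrence row is ambiguous for any patient already reduced.

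The conclusion rests on two readings: that the dose modification guidance cited in Sections 6.2.6 and 6.6.1.1 means Table 2, and that the patient is in fact at the reduced dose when the toxicity occurs. It needs no pharmacokinetic assumption. How many patients meet both conditions cannot be derived from the documents. The primary endpoint, alpha and power are untouched. This is a patient-safety clarification that should be made, and no judgement is offered here on which dose is right.

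**What to change.** Reconcile Section 6.2.4 (Table 2), Section 6.2.6, Section 6.6.1.1 and Appendix C in a protocol amendment. The revised text should state:

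1. how Table 2 applies to a patient already below 420 mg for liver impairment or a CYP3A inhibitor;
2. what the original dose level means for that patient;
3. what applies when no lower level is defined.

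Sections 6.2.6 and 6.6.1.1 should then cite Section 6.2.4 by number if that is the guidance meant. The doses and the governing rule are clinical decisions for the sponsor. The cost is a clarified table or note and two cross-references, with no new procedures or data collection and no change to the analysis.
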